#### 5.7 ANALYSIS

Analysis will proceed on two levels. Firstly, an inductive thematic analysis [32] will take place which will focus on answering the research objectives. That is, the barriers and levers of quality of prison healthcare will be explicitly drawn out alongside an understanding of what is important to the participants themselves regarding this issue. This approach will be iterative as preliminary insights gathered during fieldwork will then assist in partially shaping the resultant coding framework. The data arising from the different participants groups will be compared and contrasted, with discordant cases actively sought. We may find that the different groups of participants are in broad agreement or that their views contrast with each other. This thematic analysis will involve a process of organising the data, descriptive coding, interpretive coding, writing and theorising. *NVivo* software will be used to aid sorting and categorisation of the data.

Secondly, a conceptual analysis will be undertaken based on an existing theoretical framework pertaining to improving the quality of healthcare [33]. This framework purports that change in quality of care is dependent on a multi-level approach, consisting of: the individual (attitudinal), the group/ team (clinical microsystems and team culture), the organisation (staffing/ resource allocation), the larger system (policy/commissioning

decisions). Conducting such an analysis will allow us to understand factors that are operating at the micro, meso, macro and super macro levels. This style of analysis will allow for conceptual understandings of the data to be generated and will move beyond the descriptive approach which will be undertaken in the traditional thematic analysis stated above. The thematic analysis allows the participants voices to be heard and gives credence to their stated perceptions and experiences. The conceptual analysis moves beyond 'what the participants' said' to attempt understanding how quality of care can be improved with reference to the theoretical change management literature, and what the levers for change are. An abductive approach to analysis will be taken [34]. This involves iterative cycles of analytical interpretation between the theoretical literature and empirical data.

# 6 WORK PACKAGE 3: ASSESSING THE QUALITY OF CARE

#### 6.1 OBJECTIVE

To assess the quality of primary care provided to prisoners through statistical analysis of anonymised and routinely held healthcare records.

#### 6.2 TIMESCALE

Months 4-14 (Nov 19-Sep 20), develop algorithms for quality indicators

Months 15-19 (Oct 20-Feb 21), Data Specialist extracts data from healthcare records

Months 19-21 (Feb-Apr 21), analysis of data for quality indicators

Months 20-24 (Mar-Jul 21), write up

#### 6.3 DESIGN

We will statistically analyse routinely collected data held in healthcare records for which Spectrum CIC is the healthcare provider. Analysis will be based on the quality indicators identified in WPI. We will explore variations in the quality of care according to prisons, particular prisoner groups and conditions. These data will be analysed to determine the quality of care that prisoners received across the years for each of the quality indicators, along with the use and uptake of preventive services.

### 6.4 SAMPLING AND SETTING CONTEXT

The data will be extracted for those prisons where Spectrum CIC provide primary care services. This will be done via SystmOne Prison, the IT system that currently holds the data

for prison-based health care for all prisons in England. Spectrum CIC are currently responsible for primary healthcare in 12 adult prisons: three category A (high security); four category B (remand); five category C (training); and one category D (open). These collectively have a capacity of approximately 8,560 prisoners in total (range 280 to 1,350).

#### 6.5 DATA EXTRACTION

SystmOne Prison contains:

- prisoner demographics (automatically updated from the Prison National Offender Management System)
- health screening data from a prisoner's first reception in prison
- data related to ongoing care including morbidity data (Read codes)
- pathology results
- prescribing records

It allows transfer of records between prisons, ensuring a complete patient health record regardless of where a term is served.

The extraction of the anonymised quality indicator data will be carried out by a Data Specialist employed by and based at Spectrum CIC. The Data Specialist already has the necessary permissions and security clearance to have direct access to the records held on SystmOne Prison. The research team already has an initial agreement with Spectrum CIC to extract the quality indicators for the 12 prisons where they are responsible for healthcare. Where existing algorithms for routinely used indicators do not exist, the Data Specialist will develop algorithms to examine the receipt of recommended care and achievement of targets, under the guidance of the research team. She will then apply the algorithms and anonymise the data. Co-investigator [name] is leading this work package and will perform the statistical analysis. The data made available to [name] will be anonymised (e.g. age groups provided rather than date of birth, Index of Multiple Deprivation score rather than addresses in community).

Individual-level data including achievement of the various indicators, demographic, screening and clinical information will be obtained for the period I April 2016 to 31 March 2019.

Relevant prison-level data (e.g. prison category) will also be included for each individual. This 36 month timeframe will ensure that we encapsulate the various potential sentences of prisoners (long term through to a number of short sentences) and also include sufficient retrospective follow-up to monitor achievement of some of the indicators (e.g. QoF period). We will also account for amendments, removals and additions to quality indicators over the time frame. A Service Level Agreement will be in place between Spectrum CIC and University of Manchester (where TF is based) to transfer the anonymised data.

#### 6.6 DATA ANALYSIS

#### **ANALYSIS**

#### We will determine:

- percentage achievement of quality indicators for the prisoner population as a whole
- comparisons of percentage achievement by:
  - prison type
  - sentence duration
  - age
  - gender
  - other relevant characteristics
- whether there are systematic differences in quality for these variables

One hypothesis is that long stay prisoners are likely to have relevant quality indicators recorded in prison, whilst those serving shorter sentences (e.g. <3 months) may be overlooked or even not apply in the time they are in prison. Exploring prisoner characteristics, such as age, is particular pertinent with the growing number of elderly prisoners (both in absolute terms and as a proportion of the prison population); and the accompanying poorer health of aging prisoners [35].

An initial descriptive and Bayesian analysis will be undertaken and then multi-level logistic regression modelling and a latent variable analysis. The initial analysis will provide the necessary information (i.e. achievement numbers, rates and levels) to assess whether further analysis is appropriate (see credibility and sense checking section below for further details). Multi-level logistic regression models will identify the factors that are associated with

achievement of the quality indicators. These types of models can appropriately account for the potential correlations between outcomes at multiple time-points and between-prison variation. The initial descriptive and Bayesian analysis will provide contextual background to understand achievement levels for the quality indicators across prisons. These between-prison differences will need to be accounted for, while exploring variations in attainment. With likely strong associations between the different quality indicators, latent variable models will be developed to identify factors common across all indicators. This unifying model will explore which factors are associated with quality in care in prisons as measured by all these indicators.

#### CREDIBILITY AND SENSE CHECKING

We will compare the initial summary and descriptive analysis of the attainment rates of the indicators by prison and prisoner groups with the contextual background elicited in WPI and 2 to check the credibility of the indicators. We will also be able to triangulate and 'sense check' the data completeness and validity of our proposed indicators and findings with existing prison Health Needs Assessments (HNAs) via our links with the Health and Justice commissioning teams and the prison health care provider. In addition, a Bayesian analysis will allow us to estimate the false negative and positive rates of the attainment rates for the prisons and prisoner groups, which would provide further information on the completeness and reliability of the data [36]. We will also compare the QoF-based quality indicator achievement rates for these prisons with published QoF rates to assess the quality of healthcare of prisoners relative to current community primary care.

Furthermore, as part of the contract management process between commissioners and prison healthcare providers, Spectrum CIC extract data quarterly for the North of England Commissioning Support Unit (NECSU). NECSU is then responsible for processing these data to provide a dashboard for providers and commissioners. The research team will have access to these anonymised dashboards for Spectrum, via NS and an appropriate Service Level Agreement. These dashboards are likely to include some of our planned quality indicators, thereby allowing a quality control comparison with data extracted and processed by the Data Specialist at Spectrum.

The length of sentence and the potential number of sentences over the timeframe needs to be considered when assessing achievement of the quality indicators. For example, if someone is diagnosed with hypertension and their blood pressure is measured and treated whilst in the community, they might not require monitoring while in prison for a short sentence (e.g. couple of months). Therefore, the timing, duration and number of sentences for each person will be important to consider when assessing achievement of particular quality indicators.

#### 6.7 SAMPLE SIZE CONSIDERATIONS

This WP aims to explore variations in the quality of primary care provision for prisoners. As such a formal sample size calculation is not appropriate as the aim is to describe the current provision. However a consideration of the characteristics of the study population shows the potential to explore the variation in prisoner groups and prisons. Taking a potential health condition with a relatively low prevalence - mental illnesses (schizophrenia, bipolar affective disorder and other psychoses), we would expect 77 prisoners to be diagnosed from the 11 prisons (0.9% prevalence based on QoF for England 2015-16). This expected number of prisoners diagnosed does not take into account the probable higher prevalence in prisoners nor the throughput of prisoners which would increase the sample population over the 3 years and so those diagnosed. For example, as a remand prison Durham has on average 60% of prisoners transferred within 50 days. If we use the lowest achievement (49%) of the QoF indicator 'The percentage of patients with a comprehensive care plan documented in the record, in the preceding 12 months', we would expect 38 of the 77 prisoners to achieve the QoF indicator. If we use the rule of thumb that logistic models should be used with a minimum of 10 events per factor/predictor variable, based on simulation studies [37], then we would be able to explore approximately three factors simultaneously as to whether they are associated with achievement of the indicator. Furthermore, using multi-levels and latent models, will likely result in the number of records required to be reduced and allow more factors to be explored with the same number of records. Therefore even with the lowest prevalence of both the condition and achievement of indicator, based on community data, we have potentially a more than sufficient study population size to explore the factors associated with variation in quality indicators.

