#### 3.2 SETTING

WPI and 2 both take place in the community. The prison healthcare records analysed quantitatively in WP3 will be drawn from the cohort of prisons for which Spectrum CIC is the lead provider of prison healthcare. The records will be extracted at Spectrum CIC headquarters based in Wakefield, not in the individual prisons. The records will be anonymised and then analysed by the statistician ([name]) at the University of Manchester, following appropriate Service Level agreements being put in place. WP4 takes

place in the community. Healthcare records that will be analysed in WP3 may relate to a prisoner having resided in any of the following establishments for which Spectrum CIC provide healthcare:

- HMP Full Sutton (male, category A and B, East Yorkshire)
- HMP Styal (female, closed, Cheshire)
- HMP Preston (male, category B, Lancashire)
- HMP Kirkham (male, category D, Lancashire)
- HMP Lancaster Farms (male, category C, Lancashire)
- HMP Durham (male, category B, County Durham)
- HMP Frankland (male, category A, County Durham)
- HMP Holme House (male, category C, County Durham)
- HMP Kirklevington Grange (male, category D, North Yorkshire)
- HMP Low Newton (female, closed, County Durham)
- HMP Northumberland (male, category C, Northumberland)
- HMP Liverpool ((male, category C, Merseyside)

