#### QUANTITATIVE DATA

The quantitative data was extracted from all prison healthcare records held at 13 prisons for the years 2017-2020. Data will be analysed for three subgroups:

The proportion of the population across 13 prisons:

- (i) with any mental health diagnosis
- (ii) prescribed any psychotropic drugs
- (iii) with any mental health diagnosis NOT prescribed a psychotropic

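### Section 6.7 says multi-level and latent models will reduce the records needed; for prison type and gender, precision is limited by the number of prisons, not records

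*Protocol*

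**What the plan says.** Section 6.7 declines a formal sample size calculation and works an example instead. At 0.9% prevalence it states that "we would expect 77 prisoners to be diagnosed from the 11 prisons". It takes 49% achievement, which gives 38 events, and at 10 events per predictor arrives at about three factors. It then adds that "using multi-levels and latent models, will likely result in the number of records required to be reduced and allow more factors to be explored" and concludes that the population is more than large enough to study factors associated with variation.

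Section 6.6 plans "comparisons of percentage achievement by" prison type, sentence duration, age and gender, among other characteristics. It asks whether differences on these variables are systematic and fits multi-level logistic models to find factors associated with achievement. It also says that between-prison differences must be allowed for. Section 6.5 treats prison category as prison-level data.

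Section 3.2 lists twelve single-sex prisons. Two are for women: "HMP Styal (female, closed, Cheshire" and "HMP Low Newton (female, closed, County Durham". The other ten are for men. Section 7A.5 repeats the approach for the mental health subgroups and counts gender among individual characteristics that may affect achievement.

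**The concern.** The worked example treats records as independent. Adding a random intercept for prison recognises that records from one prison resemble each other. For a factor that takes one value throughout a prison, this adds between-prison variance to the standard error, so more records are needed to reach a given precision, not fewer. Beyond some point, extra records bring almost no gain, because the replication that counts is the number of prisons.

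This affects what can be concluded. In the listed set, a female-male difference is a difference between two sites and ten others. Whatever is particular to the two women's prisons cannot be told apart from being female. In section 7.4, step (a), the panel sets priorities partly from prisoner groups with lower achievement. If the gender effect is read as individual-level and precisely estimated, the panel could direct improvement at women as patients when the cause is local practice at two sites, or the reverse.

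**Working it through.** **The plan's own figures.** Capacity (section 6.4): "These collectively have a capacity of approximately 8,560 prisoners in total (range 280 to 1,350". 8,560 × 0.009 = 77.0 diagnosed; 77 × 0.49 = 37.7, or 38 events; 38 / 10 = 3.8, taken as about three factors. All reproduce. The inference drawn from them is what fails.

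**Inputs.** Twelve prisons, 2 for women and 10 for men (section 3.2); achievement p = 0.49 and 77 records (section 6.7), so m = 77 / 12 = 6.4 records per prison. The documents give no ICC, so 0.01 to 0.10 is assumed.

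**Formulas.** For a random-intercept logistic model:

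- between-prison variance: tau² = ICC × (π²/3) / (1 − ICC)
- variance of the female-male log odds ratio: (tau² + 1/(m p (1 − p))) × (1/2 + 1/10)
- as m grows, the standard error tends to tau × √0.6 = 0.775 tau
- narrowest 95% interval: odds ratio divided and multiplied by exp(2.228 × floor), with t on 12 − 2 = 10 df
- design effect for the 77 records: 1 + (6.4 − 1) × ICC

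| Assumed ICC | 0.01 | 0.02 | 0.05 | 0.10 |
|---|---|---|---|---|
| tau² | 0.033 | 0.067 | 0.173 | 0.366 |
| Floor on SE, gender (2 v 10) | 0.141 | 0.201 | 0.322 | 0.468 |
| Least interval factor (t, 10 df) | 1.37 | 1.56 | 2.05 | 2.84 |
| Floor on SE, even split (6 v 6) | 0.105 | 0.150 | 0.240 | 0.349 |
| Design effect, 77 records | 1.05 | 1.11 | 1.27 | 1.54 |
| Independent-record equivalent of 77 | 73 | 69 | 61 | 50 |

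The 6 v 6 row is the best that any two-group contrast of twelve prisons can do, so it bounds a two-way prison-type comparison.

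**How the standard error behaves as records are added (ICC 0.05, gender).**

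| Records per prison | 6.4 | 100 | 700 | 7,000 |
|---|---|---|---|---|
| SE allowing for prison | 0.691 | 0.358 | 0.328 | 0.323 |
| SE treating records as independent | 0.612 | 0.155 | 0.059 | 0.019 |

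A simulation at ICC 0.05 (4,000 data sets per size) gave empirical standard errors of 0.715, 0.392, 0.326 and 0.320 at 6, 50, 700 and 5,000 records per prison. This agrees with the floor of 0.322 within simulation error.

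**Number of prisons.** Section 6.7 uses 11, section 6.4 says that "Spectrum CIC are currently responsible for primary healthcare in 12 adult prisons" (its category counts, 3 + 4 + 5 + 1, sum to 13), and section 7A.4 says that "The quantitative data was extracted from all prison healthcare records held at 13 prisons for the years 2017-2020". One men's prison fewer or more changes the multiplier from 0.775 to √(1/2 + 1/9) = 0.782 or √(1/2 + 1/11) = 0.769, which is immaterial.

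**The case against.** The sentence is hedged, covers latent models as well, and names neither gender nor prison type. Much of this stands. Age and sentence duration vary within prisons and have no such floor. Pooling strongly related indicators in a latent model can add information per person, though it adds no prisons. Compared with one indicator variable per prison, a random intercept saves parameters: 11 such variables would need 11 × 10 = 110 events under the plan's own rule, against 38 available. But the calculation in section 6.7 contains no prison terms, so this is not a saving relative to that calculation. A reader might infer that the sentence is false throughout; the documents support only that it is unsupported, and reversed in direction for prison-level factors.

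It can also be said that the aim is descriptive. A description of these particular prisons, with no inference beyond them, has no such floor. Section 6.6, however, asks about systematic differences and associated factors, and section 6.7 itself applies a rule for regression models.

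Three further inferences are tempting and go too far:

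- **Tests will reject too often.** The protocol names no test, estimation method or reference distribution for these terms, and it plans a Bayesian stage, so no error rate can be attached to it.
- **Gender and prison type enter one model and are exactly collinear.** The protocol does not say that both enter together, and section 6.4 classifies all prisons as A to D with no female type. They coincide only if women's closed prisons are coded as a type.
- **The whole capacity shrinks to a few hundred effective records.** The worked example in section 6.7 has 77 records, and the loss there is moderate.

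Transfers between prisons mean one person may contribute to more than one type. Type is still replicated only across prisons.

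**Conclusion.** The point holds for prison-level factors. Section 6.7 uses an unsupported statement to help justify its conclusion on size, and for prison type and gender the statement runs the wrong way. For gender, even unlimited records leave a standard error of at least 0.14 to 0.47 and a 95% interval of at least a factor of 1.37 to 2.84 either side of the odds ratio. The 77 records of the example are worth about 73 to 50 independent ones for such a factor.

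These sizes rest on the assumed ICC range of 0.01 to 0.10, on a random-intercept model, and on the list of two women's and ten men's prisons. The existence of a floor needs only a between-prison variance above zero, which section 6.6 itself anticipates. The extracted data may still be ample for within-prison factors; nothing here shows otherwise.

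**What to change.** - **Section 6.7:** remove the sentence, or restrict it to factors that vary within prisons. State that prison-level comparisons are limited by the number of prisons behind each level, and give that number for each (two for women).
- **Sections 6.6 and 7A.5:** report gender as a contrast between the two women's prisons and the men's prisons, not as an individual-level effect. Do not interpret gender and prison type as separately estimated where they coincide.
- **Intervals for prison-level terms:** base them on between-prison degrees of freedom, or on a Bayesian model with a stated prior on the between-prison standard deviation.
- **Number of prisons:** reconcile the counts of 11, 12 and 13 so that the replication behind each comparison is clear.

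No new data are needed. The cost is some rewording and wider intervals for prison-level terms; age and sentence duration can stay as planned.

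### Section 6.7 treats the lowest achievement rate as the hardest case, but the rarer outcome limits a logistic model, so its adequacy claim does not hold for small-denominator indicators far from 50% achievement

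*Protocol*

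**What the plan says.** Section 6.7 of the protocol declines a formal sample size calculation because the aim is descriptive, and gives a feasibility argument instead.

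- It takes serious mental illness as a low-prevalence condition ("0.9% prevalence based on QoF for England 2015-16") and states "we would expect 77 prisoners to be diagnosed from the 11 prisons".
- It chooses what it regards as the least favourable rate: "If we use the lowest achievement (49%) of the QoF indicator" on documented care plans. From this, "we would expect 38 of the 77 prisoners to achieve the QoF indicator".
- It applies a rule of ten events per predictor and concludes that "we would be able to explore approximately three factors simultaneously as to whether they are associated with achievement of the indicator".
- It adds two caveats without figures. The 77 leaves out the likely higher prevalence in prison and three years of throughput, and multi-level and latent models are expected to need fewer records.
- It closes with the general claim: "Therefore even with the lowest prevalence of both the condition and achievement of indicator, based on community data, we have potentially a more than sufficient" number of records for exploring variation in the indicators.

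Section 6.6 names prison type, sentence duration, age and gender, plus other characteristics, as comparison variables, and asks "whether there are systematic differences in quality for these variables". It also says that the initial analysis will show whether modelling is appropriate for an indicator, but sets no threshold.

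**The concern.** The closing claim works only if model capacity grows as achievement rises, so that any indicator above 49% is easier to model than the example. That is not how the rule behaves. Modelling achieved is the same as modelling not achieved with the signs of the coefficients reversed, so the rarer of the two outcomes sets the limit. At 49% the two are almost equal, and the stated worst case is close to the best one.

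The rule is also counted per factor, whereas it limits estimated coefficients. A factor with several categories uses several.

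This is the only adequacy reasoning in the protocol. Someone applying it would regard a well-achieved indicator with few eligible prisoners as safe for a multi-factor model, when it may have only a handful of non-achievers. The resulting odds ratios would be unstable. Groups with lower achievement are what the WP4 panel reviews when it sets priorities (section 7.4, step a), and WP5 repeats the modelling approach for mental health subgroups (section 7A.5).

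**Working it through.** **Inputs from the protocol.** Capacity is from section 6.4: "These collectively have a capacity of approximately 8,560 prisoners in total". Prevalence 0.9%, achievement 49% and ten events per predictor are from 6.7. The four named variables are from 6.6, and the prison categories A, B, C and D from 6.4. Every achievement rate other than 49% below is an assumption, shown as a range.

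**Reproducing the plan's figures.**

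- Diagnosed: 8,560 × 0.009 = 77.04, so 77.
- Achievers: 77 × 0.49 = 37.7, so 38.
- Factors: 37.7 / 10 = 3.8, so three whole factors.

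All three agree with 6.7. (Section 6.4 gives the 8,560 for 12 prisons and 6.7 refers to 11. That is a separate inconsistency and does not affect this point.)

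**Capacity with the rarer outcome as the limit.** Supported parameters = N × min(p, 1 − p) / 10, where p is the achievement rate. With N = 77:

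| Achievement | Achieved | Not achieved | Counting achievers only | Rarer outcome |
|---|---|---|---|---|
| 10% | 7.7 | 69.3 | 0.8 | 0.8 |
| 30% | 23.1 | 53.9 | 2.3 | 2.3 |
| 49% | 37.7 | 39.3 | 3.8 | 3.8 |
| 50% | 38.5 | 38.5 | 3.85 | 3.85 |
| 70% | 53.9 | 23.1 | 5.4 | 2.3 |
| 80% | 61.6 | 15.4 | 6.2 | 1.5 |
| 90% | 69.3 | 7.7 | 6.9 | 0.8 |

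The two counts agree up to 50% and then diverge. At 90%, counting achievers gives 6.9 parameters where the rarer outcome supports 0.8.

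**Range over which three parameters are supported.** Thirty rarer outcomes are needed: 30 / 77 = 0.39, so achievement must lie between about 39% and 61%.

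**Records needed for three parameters.** N = 30 / min(p, 1 − p):

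- 70%: 30 / 0.3 = 100
- 80%: 30 / 0.2 = 150
- 90%: 30 / 0.1 = 300

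**The variables in 6.6.** Four variables need at least four parameters, hence 40 rarer outcomes. The most that 77 records can supply is 38.5. If prison type is entered as four categories it takes three parameters, which uses the whole allowance at 49% before sentence duration, age or gender is added.

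**Sensitivity to a larger N.** Doubling to 154 gives 154 × 0.2 / 10 = 3.1 at 80%, but 154 × 0.1 / 10 = 1.5 at 90%. Quadrupling to 308 gives 308 × 0.1 / 10 = 3.1 at 90%, but 308 × 0.05 / 10 = 1.5 at 95%.

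**Large denominators.** An indicator that applies to all 8,560 prisoners at an assumed 90% has 856 non-achievers, or about 85 parameters on the same rule.

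**The case against.** The strongest case for the plan has four parts.

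1. **77 is a floor.** Section 6.7 says that it leaves out higher prison prevalence and throughput. This stands, and any restated figure should say so. But neither effect is quantified, and the sensitivity figures show that even a large multiple leaves some achievement rates short.
2. **Many indicators concern common topics.** Section 4.5 includes hypertension and smoking, where denominators will be far larger. This also stands and limits the point to sparse indicators.
3. **Section 6.6 already provides a check before modelling.** It does, and it is the right place for one. It has no criterion, however, and the only reasoning available to apply it counts achievers rather than the rarer outcome.
4. **Little depends on this paragraph.** The aim is exploratory, the closing claim is hedged, the records are routine and no recruitment target rests on it. In the current version, section 7A.4 describes the data as already extracted. This lowers the severity but does not make the inference right.

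The expected saving from multi-level and latent models comes without a figure, so it cannot carry the claim.

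A reader might infer that the printed calculation is wrong, or that the claim fails in its own worked example. Neither is supported: 77, 38 and about three factors are correct at 49%. A reader might also infer that WP3 is too small for high-achievement indicators in general. The document does not support that either, because the shortfall needs a small denominator as well as an extreme rate, and the protocol nowhere pairs a rate of 70% or more with a 0.9% condition.

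**Conclusion.** The arithmetic in 6.7 is correct, but the inference drawn from it is not. For a fixed number of records, 49% achievement is almost the most favourable case. The general adequacy statement does not hold for indicators with few eligible prisoners and achievement well away from 50% in either direction. If 49% really is the lowest rate, the exposure lies entirely on the high side. If achievement in prison is lower than in the community figures, it lies on the low side as well. Even in the worked example, about three parameters fall short of the four variables named in 6.6.

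The sizes rest on 77 records, on the plan's own ten-per-predictor rule and on assumed achievement rates. The rule is rough, so the figures show direction and order of magnitude rather than exact requirements. For an exploratory analysis of routine records this is a correction that should be made, not one on which the study depends.

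**What to change.** 1. In 6.7, apply the rule to the smaller of achieved and not achieved, and count estimated parameters rather than factors.
2. Replace the closing sentence with the supported parameters over a range of achievement rates, labelled as the floor at 77 records: 3.8 at 49%, 2.3 at 70%, 1.5 at 80% and 0.8 at 90%. Add that three parameters need about 100, 150 and 300 records at 70%, 80% and 90%. State that throughput and higher prison prevalence would raise the number of records by an amount not yet quantified.
3. In 6.6, make the existing check on whether to proceed to modelling use the actual rarer-outcome count for each indicator. Where that count is too small for the planned model, report descriptive or penalised estimates. The detail can sit in the analysis plan. Since the data are described as extracted, the real counts can be used directly.

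The cost is a less favourable stated figure and fewer model terms for some sparse indicators. No further data are needed.
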